The findings from our research will be shared with both the Ministry of Health (MoH) and MOGE and will guide Zambia's national strategic plan for improved uptake and retention of SRH services by adolescents. We are working closely with these partners and Lusaka District Education Board Secretary to pave the way for complete integration of the SKILLZ Package into the public education system should this intervention prove effective. Our team will work closely with the MOH and MOGE throughout study implementation to ensure that services are integrated, streamlined and sustainable as well providing guidance on sustainable forms of distribution at the community level.

c. Overall purpose of the research and area/site where the research will be conducted

As part of routine activities, GRS is already implementing an approved, school-based curriculum at the majority of secondary schools in Lusaka however, it is unclear as to whether this curriculum, in itself, will improve health seeking behaviors and ultimately decrease HIV infection and unintended pregnancies amongst this high-risk group.

The overall purpose of the research is to assess the impact of the enhanced SKILLZ GIRL Package, including different components of the program aimed at both HIV-infected and uninfected adolescent school girls over two years on the outcomes of (1) HIV testing and subsequent retention in care, and (2) contraceptive uptake and continuation for pregnancy prevention. We will also assess the impact of school-based SKILLZ clubs, on 1) HIV testing and subsequent retention in care, and (2) contraceptive uptake and continuation for pregnancy prevention. The study will take place across several high density population areas of Lusaka where CIDRZ supports government MoH clinics with ARV services, electronic data management, and youth-friendly trained clinical personnel and where GRS has been implementing their basic SKILLZ curriculum and events in secondary schools.

2. Statement of the problem

a. Short summary of the background on the problem

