2. **Enhanced SKILLZ-Girl** is based on the curriculum described however we have modified the regular SKILLZ-Girl curriculum to include a focused module on HIVST, PrEP and contraception. In our study we will be comparing the 'regular' SKILLZ girl curriculum with this 'enhanced curriculum. The enhanced curriculum is based on the same premises and methodology as SKILLZ-girl.

Both SKILLZ-Girl and SKILLZ-Girl enhanced focus on building adolescent girls' health and social assets, culminating in a soccer tournament to address detrimental social norms and attitudes towards girls and disrupt traditional service delivery models with several salient features:

- *Building individual self-efficacy, empowerment and future orientation through the SKILLZ-Girl and enhanced curriculum:* A series of 10-12 x 1.5-hour sessions will be delivered by coaches (1 coach for every 25 girls) over approximately 12 weeks at school during normal school hours. The curriculum validates experiences of puberty and sexuality while building life skills and other critical assets that are broadly applicable to many spheres of girls' lives. It provides a link to a range of behavioral outcomes including stigma prevention, SRH and contraception, all designed to create an integrated health package for young women. The curriculum culminates in a soccer event where participants will be offered an opportunity to either test for HIV at the event or (depending on intervention arm) take home a HIVST kit, take up a contraceptive method or be assessed for uptake of PREP. The Permanent Secretary for MOH has provided support to conduct this assessment particularly in improving access to PREP for at-risk adolescent girls (*see Appendix C*).
3. Following the community soccer event, in the enhanced arm, all girls (regardless of HIV or testing status) will be invited to participate in **SKILLZ-Club**. These school-based clubs are run in the afternoons during extra-curricular hours and provides students with an opportunity to continue to engage in a deeper discussion about SRH, empowerment, HIV prevention and HIV testing. SKILLZ-Club also focuses on contraception initiation and continuation as a tool for future planning, self-care and empowerment. It also includes participation in a community change project that continues to build self-efficacy and agency. The club is an

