Within SKILLZ-Girl and SKILLZ-Club, our study will examine the additional benefits of offering access to two new health service offerings that are expressly designed to overcome barriers to uptake especially difficult for adolescents to overcome—HIV self-testing (HIVST) kits and access to an expanded method mix for contraceptive methods. Referral for contraceptive and SRH services will be made to the PEPFAR-funded DREAMS Houses or youth corners at local government facilities which are located within close distance to all schools where the SKILLZ package will be implemented.

Our mixed-methods evaluation will assess the effects of the enhanced SKILLZ offering (SKILLZ-Girl Enhanced & SKILLZ Club programs) compared to the SOC SKILLZ offering of SKILLZ-Girl only. Although the SKILLZ Program (Enhanced or SOC pending school allocation) will be offered to all girls enrolled in Grade 10 at selected study secondary schools, only girls aged 16 and over at the commencement of SKILLZ-Girl will be enrolled into the research study.

We will examine outcomes for school girls aged 16 and over enrolled in Grade 10 at the start of the intervention in up to 16 schools where the SOC SKILLZ Package is offered, compared to outcomes in up to 16 schools where the enhanced SKILLZ-Package is offered, including HIVST, the availability of expanded contraceptive services and the SKILLZ-Club following completion of SKILLZ-Girl. Therefore, all schools will be preassigned prior to the intervention into the following 2 categories (see **Figure 3** in *Section 8 - Methodology* below).

1. **SOC:** SKILLZ-Girl → Club SOC
2. **ENHANCED:** SKILLZ-Girl enhanced → SKILLZ-Club

Our central hypothesis is that the additional offering of HIVST and contraceptive services in an enhanced SKILLZ-Girl combined with the SKILLZ-Club offering will increase HIV testing and contraceptive uptake and continuation.

In addition to SKILLZ-Girl and SKILLZ-Club, girls testing HIV-positive at any time during the study intervention period will be additionally offered to participate in the SKILLZ-Plus facility-based curriculum for HIV-infected adolescents. The effect of the SKILLZ-Plus curriculum will be tested using a SmartCare-derived matched (i.e., on clinic, age, ART start date and gender) population.

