GRS has shown that soccer-based interventions combined with strong school and community partnerships and referral networks can change behaviors and make a significant impact on the health of young people.⁵³ In 2009 in South Africa, GRS piloted the SKILLZ-Girl program which addresses the unique needs of young women and adolescent girls. This program was then scaled in South Africa and expanded further into 13 countries in SSA. A recent evaluation of the SKILLZ-Girl program showed that participants significantly improved their knowledge and attitudes surrounding HIV risk for young women, negotiation skills, and sense of self-efficacy. In fact, 68.5% of girls that participated in the SKILLZ-Girl program underwent testing for HIV at the conclusion of the school-based curriculum.⁵⁴ Although SKILLZ-Girl has now served over 26,000 girls in 14 countries, it has never been rigorously evaluated for cost effectiveness and effectiveness.

6. Research questions

Our mixed-methods evaluation aims to assess the effect of the enhanced SKILLZ- girl on HIV testing and SRH related prevention services uptake (Aim 1), the effect of SKILLZ-Plus on HIV retention to care and VLS amongst HIV-infected girls (Aim 2) and identify mediating pathways and moderating factors leading to observed effects (Aim 3). Aim 3 will also assess the cost-effectiveness of the SKILLZ Package.

Our research questions are thus:

- a. What is the impact of enhanced SKILLZ-Girl vs regular SKILL-girl curriculum on HIV testing uptake among adolescent girls (aged 16 and over) over a 24-month period?
- b. What is the impact of enhanced SKILLZ-Club on HIV testing uptake among adolescent girls (aged 16 and over) over a 24-month period?
- c. Among HIV-positive adolescent girls, what is the impact of the SKILLZ-Plus intervention on:
 - a. retention in care and treatment at 6, 12, and 24 months
 - b. viral load suppression at 12 months?

- d. What specific barriers to access to services do the SKILLZ interventions (SKILLZ Girl, enhanced SKILLZ-girl, SKILLZ-Club & Plus) overcome?
- e. What are the mediators of the observed effects?
- f. What are the moderators of the observed effects?
- g. To what degree was the intervention implemented per protocol (fidelity)?
- h. What is the short- and long-term cost-effectiveness of the SKILLZ Package intervention?

7. Research aim(s)/General Objective and Specific Objectives

Aim 1: Assess the impact of SKILLZ over two years on:

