Cluster randomized controlled trial: We will select up to 18 (2 pilot + 16 for full implementation) schools from the Urban District of Lusaka to receive the SKILLZ-Girl curriculum. Of the total (up to 18), half will be randomly allocated to host the standard SKILLZ-Girl curriculum, and the remaining half (e.g., up to eight) will be randomized to either enhanced SKILLZ-Club. Those schools randomized to standard SKILLZ Girl curriculum will only have access to SOC clubs. Those schools selected for enhanced SKILLZ Girl curriculum will offer SKILLZ Club. See **Figure 3** for study allocation flow.

Figure 3. School Selection Flow Chart

[figure not shown]
ONGOING REFERRAL TO COMMUNITY CARE FOR SERVICES

We anticipate that most of our evaluation cohort will not be HIV-infected. Thus, the retention to SRH analysis drives the sample size calculation of 351 girls using contraception at the end of two years, with, and risk ratio difference of 0.3 (30%) between the SOC and enhanced SKILLZ-Club schools. To realize the 351 needed to meet requirements for estimate sensitivity, we augment the initial sample size receiving the SKILLZ-Girl curriculum accounting conservatively for 25% uptake of SRH methods and multiplying by two to assess the difference within each SKILLZ-Girl model (phase 1) and accounting for attrition across the two years of follow-up (12.5%) resulting in a starting sample size of 3159 $((351/0.25) \times 2) \times 1.025$. **SKILLZ-CLUBS** will act as an extension to the SKILLZ-Girl curriculum enabling participants to seamlessly transition from the SKILLZ-Girl curriculum into the SKILLZ-Club. We anticipate minimal attrition (~15-20%). Participants will spend the majority of the study window in SKILLZ-Club and it is through the SKILLZ-Club affiliation that we will follow-up and ascertain outcomes for those enrolled longitudinally.

For the small minority of girls found to be HIV-infected across all schools where the study will be conducted, we will evaluate linkage to care and on treatment, VLS, and retention in care for a period of two years. These girls will be encouraged to continue on to the HIV positive-specific SKILLZ-Plus facility-based curriculum. We will quantitatively measure the impact of SKILLZ-Plus on linkage to care and treatment, retention and viral load at 6, 12, and 24 months after diagnosis (or since participant is identified by GRS as HIV+) using SmartCare data and compare to an existing matched cohort.

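### Research questions a and b ask for separate 24-month effects of enhanced SKILLZ-Girl and SKILLZ-Club, but the two-arm design estimates only the combined package

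*Combined protocol and SAP*

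**What the plan says.** Section 6 separates the components. Question a reads "What is the impact of enhanced SKILLZ-Girl vs regular SKILL-girl curriculum on HIV testing uptake among adolescent girls", and question b reads "What is the impact of enhanced SKILLZ-Club on HIV testing uptake among adolescent girls (aged 16 and over) over a 24-month period". Both run over 24 months. Section 1c first gives the effect of the enhanced package as the overall purpose and then adds: "We will also assess the impact of school-based SKILLZ clubs, on 1) HIV testing and subsequent retention in care". The same sentence extends to contraceptive uptake and continuation. Section 8d says the surveys after the event will be used to assess both SKILLZ-Girl and SKILLZ-Club.

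The allocation does not separate them. Section 4 gives the SOC sequence as "SKILLZ-Girl → Club SOC" and the other arm as the enhanced curriculum followed by SKILLZ-Club. Section 8c fixes the pairing at school level: "Those schools selected for enhanced SKILLZ Girl curriculum will offer SKILLZ Club", and "Those schools randomized to standard SKILLZ Girl curriculum will only have access to SOC clubs". Within enhanced schools nobody is held back from the Club: "Following the community soccer event, in the enhanced arm, all girls (regardless of HIV or testing status) will be invited to participate in" SKILLZ-Club (section 4, item 3).

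Section 8f defines the primary outcome as any HIV test from programme delivery to 24 months after the final event. It is modelled with a study-arm indicator interacted with one before/after indicator. No Club term appears.

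**The concern.** The objectives promise two answers and the allocation supplies one. If question b is meant as a Club effect distinct from the curriculum effect in question a, no randomised comparison corresponds to it. Question a over 24 months has the same problem in reverse, because by then the enhanced-arm girls have also been offered the Club.

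What is at stake is what the trial may conclude. An arm difference at 24 months supports a statement about the whole package. It does not support a statement that clubs raise testing, or that the enhanced curriculum does so without clubs. As sections 1c, 6 and 8d are worded, a report could make either statement.

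**Working it through.** **1. The plan's own power figure, to see which contrast it covers.** Inputs from section 8c: 60% versus 80% tested, alpha 0.05 (taken as two-sided; the plan does not say), 80% power, ICC 0.1, about 100 girls per school, up to 18 schools (9 per arm).

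- Unclustered n per arm = (1.96·√(2·0.7·0.3) + 0.8416·√(0.24 + 0.16))² / 0.2² = (1.270 + 0.532)² / 0.04 ≈ 81.2, so 82.
- Design effect = 1 + (100 − 1)·0.1 = 10.9. Then 82·10.9 = 893.8 girls per arm, or 8.94 schools, so 9 per arm.
- Power at 9 per arm: effective n = 900/10.9 = 82.6, giving 80.7%. At 8 per arm (the 16 full-implementation schools): 800/10.9 = 73.4, giving 75.8%.

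The figure reproduces. It is the power of a single two-arm contrast, before attrition.

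**2. What the 24-month contrast contains.** Let g24 be the effect of the enhanced curriculum and event at 24 months, given that the girl has had them, and c24 the added effect of the Club.

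- SOC schools: mean = μ.
- Enhanced schools: mean = μ + g24 + c24.
- Difference: D24 = g24 + c24.

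Across schools the enhanced-curriculum indicator and the Club indicator are identical. A design matrix with an intercept and both indicators has 3 columns and rank 2. In a 2×2 allocation it would have rank 3. Adding schools or girls does not change the rank.

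**3. What the post-event survey adds.** If it is completed before clubs begin, the arm difference then is D0 = g0, the short-term effect of curriculum plus event. The later change is

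D24 − D0 = (g24 − g0) + c24.

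A three-period difference-in-difference has 7 parameters: two arm levels, two period effects, g0, the change in g after the event, and c24. There are 6 cell means and the rank is 6. Fixing g24 = g0 removes one parameter, and then c24 = D24 − D0. With a third arm (enhanced curriculum without the Club) the rank is 8 of 8.

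*Illustration.* Take D24 = 80 − 60 = 20 points and assume D0 = 10. The later 10 points could be 10 from the Club and 0 from delayed curriculum or event effects, or 0 and 10. If the curriculum effect fades, the Club share exceeds 10. Take-home HIVST kits (section 4) give a concrete route for a delayed effect: a kit handed out at the event may be used after the survey.

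**4. Could a Club contrast be built from the existing schools?** Splitting 8 enhanced schools 4 versus 4 gives an effective n of 400/10.9 = 36.7 per group. Power for 60% versus 80% = Φ((0.2·√36.7 − 1.270)/√0.40) = Φ(−0.09), about 46%. The effect size is an assumption, since the plan gives none for the Club on HIV testing.

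**The case against.** **Question b may mean the package.** It does not say the Club alone and names no comparator, and section 8c's sample-size text uses the enhanced Club as a label for one arm. On that reading b compares enhanced-Club schools with SOC schools, which the design does estimate. But a and b would then be duplicates, and section 1c's additional Club objective would add nothing. Section 8c also offers a choice of Club allocation with only one option, and doubles the sample for a comparison inside each SKILLZ-Girl model. That wording points towards a separation the current arms do not provide.

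**Everything operative is at package level.** The central hypothesis (sections 3b and 4), the evaluation statement in section 4 ("SKILLZ-Girl Enhanced & SKILLZ Club" against standard SKILLZ-Girl), Aim 1(i), the HIV-testing power and the primary model all concern the package. Bundling components is legitimate in a pragmatic trial. This stands, and it limits the point to the objectives and the claims drawn from them.

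**A reader might infer that a Club effect cannot be estimated on any terms.** The documents do not support that. Clubs follow the event, and surveys are planned post-event and at 3, 12 and 24 months. A period-split estimate exists under the condition g24 = g0. That condition is strong, unstated and untestable in these two arms, but it is an assumption rather than an impossibility.

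**A reader might infer that Aim 3 contains component cost-effectiveness ratios to be withdrawn.** Aim 3 names the Girl, Club and Plus curricula, but question h refers to the SKILLZ Package, and the HIV-testing ratio in section 8f is intervention minus control. No Girl-only or Club-only ratio is specified. Nor does any text say that the same 24-month difference will be reported twice. The stated policy goal in section 1b is integration of the whole package, which the arm contrast does inform.

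**Conclusion.** The point holds as an inconsistency between objectives and design. Sections 1c, 6 and 8d commit to distinct effects of enhanced SKILLZ-Girl and SKILLZ-Club, while sections 4, 8a, 8c and 8f provide one 24-month contrast equal to their sum. Neither component has randomised support of its own over 24 months. A Club-period effect rests entirely on the assumption that the enhanced curriculum, event and kits have no changing effect after the event.

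The primary package-level inference and its power calculation are untouched.

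A short-term effect of curriculum plus event can be isolated only if the post-event survey is completed before Club sessions begin. The plan does not date that survey relative to the clubs; section 8d places the 3-month survey in Club schools during club attendance. Even when correctly timed, an early survey would miss later use of take-home kits.

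**What to change.** 1. In section 6, restate question b, and question a at 24 months, as the effect of the whole enhanced package (curriculum, event and Club) against SOC. Align the Club sentences in sections 1c and 8d.
2. In section 8f, add an arm contrast at the scheduled post-event survey as the short-term effect of enhanced curriculum plus event. State that the survey must be completed before Club sessions begin, and that take-home kits may be used after it.
3. Label any analysis of change from post-event to 24 months as descriptive or exploratory, and print the no-changing-effect assumption beside it.
4. Word Aim 3 at package level for Girl and Club, consistent with question h.
5. In section 8c, reconcile the incomplete Club randomisation wording and the doubling for a within-model comparison with the two arms actually used.

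The cost is edits to the text, one extra time-point analysis on data already planned, and a narrower claim. A randomised Club effect would need a third arm or a 2×2 allocation. Splitting the existing enhanced schools would leave that contrast underpowered even for a 20-point effect, so restating the questions is the proportionate course.

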ongoing activity that students can participate in until they leave or graduate from school. Girls participating in the SOC Arm (SKILLZ-Girl) are able to join any of the other clubs currently offered at their school (SOC Clubs).

Clubs have been operating in schools in Zambia since 2017 with the MOGE's consent as part of the Memorandum of Understanding (MOU) signed in 2010 (*see Appendix B*). The CLUB component is currently evolving to include a more formalized education component, and will be piloted in Zambia at the same time as this evaluation.

4. All girls who test positive for HIV (whether prior to the SKILLZ-Girl event, during the event or as part of their participation in SKILLZ-Club) are referred to **SKILLZ-Plus**, a clinic-based initiative which provides HIV-infected girls access to ongoing support through a 12-week curriculum. During follow-up in the SOC Club arm, study staff will refer any newly identified HIV-positive girls to SKILLZ-Plus. In addition, study staff will refer newly diagnosed girls aged 16 years from neighboring clinics to the SKILLZ-Plus intervention.

For girls who test positive for HIV, either through a:

1. school referral either at the event, during club participation, are identified during follow-up or with a previously known diagnosis or
2. clinical referral (newly diagnosed only)

In addition, all girls found to be HIV-positive at any point throughout the SKILLZ-Program will be provided with intensive counselling support. Coaches will facilitate a family visit to facilitate disclosure and work with CIDRZ networks to provide additional psycho-social support as needed on a case-by-case basis by the participant.

SKILLZ-Plus provides several additional features:

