- *Enhanced linkage to care:* HIV+ positive girls are matched with trained coaches (~6 girls per coach) who use soccer-based activities to guide participants through issues such as acceptance, disclosure, healthy living and adherence. The coach will be responsible for providing the girl with the support and the guidance she needs to access ART services at MoH clinics. This support will include both psychological support and logistical (i.e. where to go, who to see, the expected outcome of each visit, etc.) The program consists of 12 modules (conducted during intensively over approximately 6 weekends) that address different aspects of living with HIV delivered in a private, confidential and non-judgmental platform at the clinic, to individuals, during regular clinic visits. The curriculum for HIV+ girls encourages girls to have discussions about living with HIV, to make healthy life decisions, to work to achieve their goals, and to become positive role models within their community. SKILLZ-PLUS received written support from MOH in 2013 (*see Appendix C*).
- *Ongoing peer support for six months through monthly interactions and virtual forums.*
- After graduation from SKILLZ-Plus, HIV-infected adolescent girls will be *linked to support groups, which meet twice every month at health facilities when they go for clinical visits or drug refills.*
- All SKILLZ-Plus groups are led by GRS trained coaches.

CIDRZ will work closely with the MOH to ensure adolescent services are available. To accomplish this, CIDRZ will support a hybrid model of community-based services and clinic-based adolescent-friendly clinics to meet the specific demands of adolescents including HIV testing, SRH services and stigma-reducing initiatives. In addition to existing testing venues, HIV testing and mobile SRH services will be offered on site during and after the tournament and a trained nurse will be available to provide a larger set of SRH services including issuing of contraceptives (including injectables, pills, and barrier methods, emergency contraception), pregnancy tests, and STI diagnosis and treatment (pending availability of supplies). All supplies will be obtained from MoH medical stores, through established mechanisms.

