- (i) (a) **HIV testing** and (b) SRH-related prevention services uptake among adolescent girls aged 16-19 in up to 9 intervention schools (with enhanced HIVST, PrEP, and contraceptive method offerings) compared to up to 9 control schools using a quasi-experimental difference-in-difference approach; and
- (ii) **linkage to care and treatment, and viral load suppression and retention at 6, 12, and 24 months** through a cohort model using pre-existing SmartCare data on HIV+ individuals in care to match to adolescent girls aged 16 and over from the same district (Lusaka) who are identified to be HIV+ at any time during SKILLZ Girl or SKILLZ Club participation and enrolled in SKILLZ-Plus.

This will be achieved by i) using a quasi-experimental difference-in-difference approach that compares girls aged 16 and over in 9 SKILLZ control schools compared to 9 schools where enhanced SKILLZ will be delivered with the enhanced HIVST and a variety of contraceptive method offerings; and ii) through a cohort model using pre-existing SmartCare data on HIV+ individuals in care to match to adolescent girls aged 16 and over from the same district (Lusaka) who are identified to be HIV+ at any time during SKILLZ-Girl or SKILLZ-Club participation.

Aim 2: Examine how the intervention works including lessons learned for future implementation by

- (i) conducting a process evaluation to identify mediators, predictors, and barriers to uptake of the SKILLZ-Girl, Club, and Plus curricula both quantitatively through mediation and moderation analyses and qualitatively through a sequential explanatory approach using focus groups discussions, interviews and observation with coaches and girls; and by
- (ii) monitoring fidelity

Aim 3: Estimate the short- and long-term cost-effectiveness and return on investment of the SKILLZ Girl, Club, and Plus curricula for improving health outcomes for adolescent girls.

8. Methodology

a. Study design

We will conduct a mixed-methods evaluation of the SKILLZ intervention using the following approaches:

A **quasi-experimental cohort** of school-aged 16-year old and over females to be followed for a two-year period will be evaluated with a difference-in-difference (DID) approach to estimate HIV testing uptake and sexual/reproductive health services use. Primary and secondary outcomes will be measured at several

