Difference-in-difference model. The primary outcome is the probability of testing for HIV at any time during the period when SKILLZ is delivered through to 24 months after the final soccer event. The primary analysis for Aim 1 will follow a difference-in-difference (DID) effect between study arms. The outcome of interest will be regressed on an indicator of study arm assignment interacted with a dichotomous variable POST which indicates the outcome after the intervention is implemented; this differentiates baseline and end-line for each study arm, controls for any time dependent variables that might confound the effect, as well as any time-invariant observed or unobserved confounders that might differ between study arm schools. Because of this, the DID is robust to time-invariant unobservable confounders (e.g., school quality) and time trends (e.g., secular increase in testing). Our estimator relies on the assumption of common time trends across intervention and control in absence of the intervention, and of static population. Additionally, we control for baseline individual and school-level moderators that may be unbalanced at baseline after randomization. School-level controls include size, promotion rates, sex composition and repetition and dropout rates (available in the district education office) and individual girls' controls include age, grade, maternal education, HIV knowledge. Clustering by school will be accounted for by a generalized estimating equation approach. We will estimate intention-to-treat (ITT) by including all girls in the evaluation cohort assigned to each arm rather than all girls who actually participated in SKILLZ.

Individual-level matched cohort analysis for HIV-infected: The analysis will follow an individual ITT estimator among individuals found to be HIV-infected, who will then be matched (based on clinic, age, ART state date, and gender) to HIV-infected individuals in the SmartCare database. The outcomes are the proportion of enrolled HIV+ girls who linked to care, who are virally suppressed and retained in care at 6, 12, and 24 months after diagnosis of HIV+ (using national electronic HIV medical record data). We will conduct an ITT analysis for the logistic probability of being suppressed at 6, 12, and 24 months after HIV+ diagnosis, where girl is the unit of analysis. All data will be analyzed using STATA.

Process evaluation: This will involve quantitative and qualitative analyses:

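### The Aim 1(ii) HIV-positive cohort is defined inconsistently: one statement requires SKILLZ-Plus enrolment, others do not, and the analysis section leaves its denominator undefined

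*Combined protocol and SAP*

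**What the plan says.** All references are to the combined protocol and SAP.

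- **Section 7, Aim 1(ii).** Linkage, suppression and retention are to be compared with SmartCare records for girls "who are identified to be HIV+ at any time during SKILLZ Girl or SKILLZ Club participation and enrolled in SKILLZ-Plus".
- **Section 7, the paragraph after the Aim 1 bullets.** It describes the same cohort again, with the same identification window but no SKILLZ-Plus condition.
- **Section 8c.** "For the small minority of girls found to be HIV-infected across all schools where the study will be conducted, we will evaluate linkage to care". SKILLZ-Plus is optional: "These girls will be encouraged to continue on to the HIV positive-specific SKILLZ-Plus facility-based curriculum". Section 8a likewise says that enrolment is offered.
- **Section 8f, matched cohort analysis.** "The analysis will follow an individual ITT estimator among individuals found to be HIV-infected". A little further on: "The outcomes are the proportion of enrolled HIV+ girls who linked to care, who are virally suppressed and retained in care". It does not say whether *enrolled* means in the study or in SKILLZ-Plus.
- **Section 4, SKILLZ-Plus.** The modules are "delivered in a private, confidential and non-judgmental platform at the clinic, to individuals, during regular clinic visits". For the control schools: "During follow-up in the SOC Club arm, study staff will refer any newly identified HIV-positive girls to SKILLZ-Plus".

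None of these sections says how a girl who is found HIV-positive and declines SKILLZ-Plus is to be counted.

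**The concern.** Two analysts could follow this plan faithfully and use different denominators. One would keep every girl found HIV-positive; the other would keep only those who took up SKILLZ-Plus.

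The second choice conditions on a voluntary act that follows diagnosis. It also runs against the plan's own idea of ITT: for the school comparison, Section 8f counts girls by assigned arm and not by whether they took part. Because SKILLZ-Plus is delivered at the clinic, willingness to join is plausibly related to linkage, retention and suppression, which are the outcomes.

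The identification window raises a second, smaller problem. Aim 1(ii) covers girls "who are identified to be HIV+ at any time during SKILLZ Girl or SKILLZ Club participation". SOC schools have no SKILLZ-Club, so for them the window closes when SKILLZ-Girl ends.

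Section 8c refers to the Aim 1(ii) endpoints as primary, and the HIV-positive group will be small, so a few girls counted or not counted can move the result.

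**Working it through.** **No figure to reproduce.** The documents give no sample size, power, expected SKILLZ-Plus uptake or effect size for the matched HIV-positive cohort. The check is a comparison of texts, followed by an illustration with assumed inputs.

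**Step 1: who is in the cohort, by section.**

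| Place | SKILLZ-Plus enrolment required? | SOC girl diagnosed after SKILLZ-Girl? |
|---|---|---|
| Section 7, Aim 1(ii) bullet | Yes | Outside the wording |
| Section 7, following paragraph | No | Outside the wording |
| Section 8a | Not stated; SKILLZ-Plus is offered | Not excluded |
| Section 8c | No; girls are encouraged to join | Included (all schools) |
| Section 8f, ITT sentence | No | Not excluded |
| Section 8f, outcome sentence | Unclear; *enrolled* is undefined | Unclear |

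The conflict lies inside Section 7, between Sections 7 and 8c, and inside Section 8f.

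**Step 2: what the enrollee-only reading can do.** Let u be SKILLZ-Plus uptake, a the retention among acceptors and d the retention among decliners. Suppose SKILLZ-Plus has no effect.

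- Full cohort: u·a + (1 − u)·d
- Enrollees only: a
- Difference: a − u·a − (1 − u)·d = (1 − u)(a − d)

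The documents give neither u nor a − d, so both are assumptions. Difference in percentage points:

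| Gap a − d | u = 90% | 80% | 70% | 50% | 100% |
|---|---|---|---|---|---|
| −10 | −1 | −2 | −3 | −5 | 0 |
| 0 | 0 | 0 | 0 | 0 | 0 |
| +20 | +2 | +4 | +6 | +10 | 0 |
| +40 | +4 | +8 | +12 | +20 | 0 |

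Section 5 reports that almost half of adolescents who know their status leave care within two years of starting ART. That figure describes ART starters, not all girls found positive, so it does not fix any of these inputs.

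**Step 3: size of the group.** Section 8a expects about 98% of girls who test to be negative, so about 2% positive. Section 8c gives a starting sample of 3159 and, separately, about 100 girls in each of up to 18 schools (1800). It also reports 62% testing uptake in GRS programmes.

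- 3159 × 0.02 ≈ 63 if every girl tests; 3159 × 0.62 × 0.02 ≈ 39
- 1800 × 0.02 = 36 if every girl tests; 1800 × 0.62 × 0.02 ≈ 22

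At 50% retention, the 95% half-width is 1.96 × √(0.25/n): about 12 points for n = 63, 16 for n = 39 and 21 for n = 22. The shifts in Step 2 for a 20-point gap are therefore smaller than sampling error, but they are systematic and would not average out.

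**Step 4: the comparator.** Comparators come from SmartCare, are already in care, and are matched on clinic, age, ART start date and gender. Two things follow. They have all linked, so they offer no fair contrast for linkage. And a girl who never starts ART has no start date on which to match.

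**The case against.** The strongest reply is that most of the text favours the broader population. Only the Aim 1(ii) bullet carries the enrolment condition. The paragraph after it, Section 8c and the ITT sentence in Section 8f do not, and Figure 2, which is not reproduced in the text available, may settle the matter. This is fair. It means the plan cannot be said to drop decliners. It does not remove the contradiction, because the bullet is explicit and the Section 8f outcome sentence can be read in its favour.

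A reader might infer three stronger things that the documents do not support:

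- **That retention will be overstated.** This needs decliners to do worse than acceptors. That is plausible but undocumented; with no gap or full uptake the difference is zero, and with a reversed gap it is negative.
- **That SKILLZ-Plus would look effective even if it did nothing.** Step 2 compares two versions of one group, not SKILLZ-Plus with its comparator. Comparators already in care could push the contrast the other way, above all for linkage.
- **That enrolment is itself the outcome.** Section 4 also describes the modules as run over about six weekends, with coaches helping girls to reach ART services, so joining may precede linkage. Section 8d measures retention by pharmacy visits and suppression by viral load; attending a session is neither. Selection on willingness is the supportable claim.

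The SOC point is also modest. Those girls do receive SKILLZ-Girl, no section expressly excludes them, and Sections 4 and 8c point to including them. It is loose wording in Section 7 that needs correcting.

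**Conclusion.** The concern holds as an inconsistency in a stated analysis population. Section 7 defines the cohort in two ways, and Section 8f names ITT and then uses a denominator it does not define. Following the Aim 1(ii) bullet would condition on uptake after diagnosis and contradict the stated ITT.

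The possible distortion of the SKILLZ-Plus group's own retention figure is (1 − uptake) × (acceptor minus decliner retention). For an assumed 20-point gap that is 2 to 10 points at 90% to 50% uptake. It could be zero or negative under other assumptions, because neither input is documented. The net direction against the SmartCare comparators is unknown. This should be corrected before analysis; it does not show that the result would favour SKILLZ-Plus.

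**What to change.** 1. In Aim 1(ii), delete the condition of enrolment in SKILLZ-Plus.
2. Use one population, in the same words, in Sections 7, 8a, 8c and 8f: every consented cohort girl found HIV-positive from the start of SKILLZ-Girl to the end of follow-up, in either arm, whether or not she joins SKILLZ-Plus.
3. In Section 8f, define *enrolled* as enrolled in the study cohort.
4. Report linkage as a proportion of all girls found HIV-positive.
5. Make the matched retention and suppression comparison among girls who start ART, regardless of SKILLZ-Plus enrolment, and state how many never start. Describe it as a comparison among ART starters: starting ART also follows diagnosis, so it is not an ITT comparison from diagnosis.
6. Report SKILLZ-Plus uptake, and give enrollees only as a labelled secondary analysis.

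**Cost.** Items 1 to 3 and 6 are wording and reporting. Items 4 and 5 also change how the matched analysis is set up, because the matching rule cannot accommodate girls without an ART start date. The change to the denominator needs no new data permission: Section 8d already asks all participants for consent to SmartCare access. The reported figures may be less favourable than those for enrollees alone.
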